1. PROTOCOL BACKGROUND

1.1 Describe the scientific/scholarly rationale and background for your project. Describe the gaps in current knowledge your project is intended to address.

The United States is in the midst of an opioid crisis--opioid use problems (OUPs) are increasingly widespread and lethal. In 2016, more than two million Americans were diagnosed with opioid use disorder (OUD) and more than 42,000 have died of an overdose involving opioids (SAMHSA, 2019). The death rate is more than any year on record and has quadrupled since 1999 (Vice Chairman's Staff of the Joint Economic Committee, 2017.) Several effective medications are now available for treating OUD but many people, who could benefit from medication, do not receive them (Sarlin, 2018). Despite the fact that effective treatments for opioid use disorder exist, only about one in four people (28.6 percent) with this disorder received specialty treatment for illicit drug use in the past year (Center for Behavioral Health Statistics and Quality, 2017.) For those struggling with opioid addiction, compared to others dependent on drugs, “the recovery period is longer, and the chance of relapse is higher.” (Wogan, 2017.) Smith and colleagues (2010) interviewed 109 residential addiction treatment patients after

discharge and found over nine in ten patients reported a relapse, with nearly six in ten patients relapsing in first week after discharge.

Substance use impairs executive decision making and depletes defenses against impulse reactivity (Office of the Surgeon General, 2016), creating challenges for the person with an OUP to recognize the need for treatment as well as navigate the treatment entry process. Having concerned significant others, including family members (hereinafter known as CSOs) trained in best-practices and equipped with effective tools to take action is game-changing. Family members have been filling gaps in the substance use disorder (SUD) care continuum for decades, frequently without recognition from the health care system. Cycles of urgent acute care followed by discharge home with no formal support are common in the US addiction treatment system as well as waiting weeks or months to move from one level of care to the next. To fill this gap, untrained family members often have no choice but to provide life-sustaining transitional care at home. Research shows that family members make the majority of the decisions around treatment, including financial decisions (Ventura et al., 2017) and thus, have high potential to impact the trajectory of their loved one's OUP for better or worse.

One study showed that social and familial reasons were the most expressed reasons for entering drug treatment and people with substance use disorders perceive treatment entry as an important way to obtain positive contingencies in their interpersonal relationships, which further underscores the potential utility of conjoint interventions with CSOs. It also suggested that the informal pressure of one's natural social network, of which CSOs are an integral part, to be influential in improving treatment retention and abstinence (Marlowe, D. et al., 1996). Despite continued and mounting empirical support that family members and loved ones play an integral role in the success and wellbeing of individuals' engagement along the OUP care continuum and contribute to health outcomes and mortality rates, family members remain on the periphery, overlooked by our current healthcare system. Similarly, they are overlooked by entrepreneurs. There has been little innovation in tools to provide help for family members and friends of an individual with an OUP (hereinafter known as identified person or IP). The significance of this project is to address this critical gap in OUP treatment by providing evidence-based training and tools to CSOs to reduce fatal and non-fatal overdoses and to increase treatment utilization.

Since it has been shown that training a CSO in CRAFT improves ability to get a treatment-resistant individual into life-saving treatment, it is highly valuable. Furthermore, new laws around delivering medical assisted treatment (MAT) online via telemedicine provides the proposed project the opportunity to fill a gap for CSOs using online technology to help them increase their treatment resistant IP's motivation to engage in treatment and connecting them to treatment online, whether it be booking a bed or accessing telemedicine and prescriptions for MAT. The project team involves We The Village, Inc, a small business already providing support to CSOs using consumer technology, [name], creator of CRAFT, [name], research expert in the field of substance use disorders, [name], primary care physician specializing in addiction treatment, and certified CRAFT coaches. Phase One of this project will develop and refine digital delivery of two modified CRAFT (Community Reinforcement and Family Training) interventions: automated and Group CRAFT protocol (CRAFT-A) and automated CRAFT protocol with live coaching (CRAFT-C) and assess the effectiveness of the adapted CRAFT protocols with WTV's business as usual model of Peer Support Forum (PEER). The goal of the project is to deliver an innovative and effective evidence-based behavioral intervention with consumer technology to an existing and growing online audience.

Abbreviations:

OUP - Opiate Use Problem - this is opioid use that has been identified by a concerned significant other as problematic but has not necessarily been formally diagnosed as an opioid use disorder.

MAT - Medically Assisted Treatment. IP - the identified treatment-resistant person (in our case, with an OUP.) CSO - concerned significant other - this is the friend or family member of the IP.

CRAFT - Community Reinforcement and Family Training. WTV - We The Village. Live coach - trained human coach. CRAFT-C - digital CRAFT + digital or telephone live coaching. CRAFT-A - digital automated CRAFT plus digital or telephone live group. PEER - Peer support (current WTV platform.)

1.2 List the primary and secondary aims, research questions, and hypotheses.

Primary Hypothesis:

- a. At the 3-month post study intake survey, we expect that CSOs assigned to CRAFT-C will report a greater proportion of IPs entering treatment as compared to the CRAFT-A and PEER groups, and the CRAFT-A group will report a greater proportion of IPs entering treatment as compared to the PEER group.

Secondary Hypotheses:

- b. At the 2-month and 3-month post study intake survey, CSOs in all three groups will report that their relationship happiness has improved relative to baseline as measured by the Relationship Happiness Scale (RHS).
- c. At the 2-month and 3-month post study intake survey, CSOs in all three groups will self-report that their own anxiety, depression, anger and physical illness has improved relative to baseline as measured by the POMS survey, SF12 Health Survey, and the SAS-SR work subscale.
- d. At the 2-month and 3-month post study intake survey, CSOs assigned to CRAFT-C and CRAFT-A will demonstrate higher fidelity of learning CRAFT principles as compared to the CSOs assigned to the standard condition (PEER), as measured by correct answers on the revised CRAFT knowledge test.
- e. At the 3-month post study intake survey, all three groups will report similar high satisfaction (average score above 3.5 on a 5-point scale) on Usability of the website and the CRAFT-C group will report the greatest satisfaction in the Usefulness of the website relative to the CRAFT-A and PEER groups as measured by the User Satisfaction Survey.

1.3 List the primary and secondary outcomes.

The primary outcome variable that will be measured is the CSO's reporting their IP entered treatment for their OUP or received additional treatment for their OUP.

Secondary outcome variables that will be measured include CSO and IP relationship happiness; CSO's physical and mental health status; CRAFT knowledge of CSOs; and CSO's satisfaction with website content and delivery.

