3 RECRUITMENT AND SCREENING

3.1 Identify the expected number of individuals screened and the expected number of individuals consented/enrolled to reach your target sample size. If multi-site, break the total down per study site. If multi-year, break the total down per study year.

For this pilot and feasibility study we plan to enroll up to 84 CSOs

3.2 Describe how prospective participants will be identified and recruited. Include information about: how, when, where, and by whom (by position or role, not by name). Describe any recruitment materials that will be used to recruit prospective participants.

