After administering the consent quiz during the confirmation call, study staff will answer questions, review next steps, and clarify expectations. If a potential participant did not pass the consent quiz, study staff will be able to review the appropriate consent form sections and to re-administer the consent quiz. After completing the confirmation call, all eligible study participants will be considered enrolled into the study. Study staff will send via email secure Survey Gizmo links with the HIPAA authorization form, locator form and baseline survey. The HIPAA authorization form will now have an option for "I'm not sure." If someone selects the not sure option, they will be directed to call the study number to discuss their concerns or ask questions before moving forward in the enrollment process. Participants must agree to the HIPAA authorization to continue with the study. After agreeing to the HIPAA authorization, participants will click the next step link to complete the locator form. After completing the locator form, participants will click a link to complete the baseline survey. The brief locator form will request important contact information in order to locate participants for the follow-up survey and to re-engage with research and intervention activities, if needed. For participants who report they share their email address with someone else, we will ask them if they are sure it is okay for us to send information to this email address. If they say No or Prefer not to answer, they will be asked if they have a secondary email address they want to use. If someone does not complete the locator form or baseline survey, study staff will reach out to the participants to encourage them to complete these required activities. All participants will have one week to complete the enrollment process. Randomization will occur after completing the baseline survey. We will use block randomization to assign a group of three participants to each condition. We will wait till we have at least people randomized to Program A to begin the program. Participants will be informed of their assigned group after completing their baseline survey. WTV will notify participants of their randomly assigned program and the appropriate next steps for their specific program assignment. This change will allow us to conduct block random assignment computed by [name] and to allow us to equal number of people in each group throughout the study recruitment period. We will program Survey Gizmo to send the research team an automatic email when someone completes the baseline survey.

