4 STUDY PROCEDURES

4.1 Provide a detailed description of the study procedures in chronological order. As applicable, include information on: differences between the control and experimental groups, the number of follow-up visits, study visit windows, participant time commitment per activity, and the setting/location per activity.

Study procedures are outlined in the figure below. After screening eligible participants complete online enrollment, which includes providing informed consent, passing a consent quiz during the confirmation call by study staff (research assistant), agreeing to the HIPAA authorization form, and completion of the locator form and baseline survey. Participants are then randomized into one of three groups.

Participants assigned to the PEER group (Program C) will participate in an online peer support forum with other CSOs. Members of the forum post questions or comments to weekly peer-led discussions and receive responses and feedback from other CSO forum members. Members typically express concerns regarding their IP's wellbeing and ask other members to share any strategies they have employed when dealing with their IPs.

Interactions typically, are based either in 12-Step strategies members have learned (usually through Al-Anon or Nar-Anon Family Groups or Family Training Workshops provided by treatment programs) or in CRAFT skills learned (usually from treatment programs or other We The Village members). A staff member from We The Village monitors forum interactions to ensure members are interacting respectfully. This individual also will report any adverse or severe adverse events that members mention online.

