● Weekly sessions follow a specific course outline and schedule	● Weekly sessions are tailored to the individual study participant	● Engagement can occur at any time of the day or night
		● Benefit from the extensive database of shared peer experiences

4.2 Briefly describe the sources or measures that will be used to collect data about participants. As applicable, include information on: instruments or surveys that will be administered, tests that will be performed, and the time points when each data will be accessed or obtained.

Data collected directly from participants:

Similar to screening and consent procedures, data collection for baseline, 8-week, and 12-week post enrollment follow-up surveys will be self-administered using Survey Gizmo software since participants may be located anywhere across the country. Participants will be directed to a separate link to complete the locator form and baseline survey after they complete the following steps:

1. Provide informed consent
2. Pass the consent quiz
3. Speak with a study staff person during the confirmation call
4. Agree to HIPAA authorization form

We will include a message that informs participants of the time estimate for completing the baseline survey, as well as the content of the baseline survey. They will be told that their contact information will be stored separately from the rest of the survey and never be directly connected to their survey answers. The baseline survey consists of socio-demographic questions, such as gender, age, race/ethnicity, and other standardized socio-demographic measures adapted from the GPRA instrument and the National Survey on Drug Use and Health. The questions in the 8-week and 12-week follow-up surveys will ask the same questions. The 8-week follow-up survey will enable the research team to assess changes in the lives of participants in an earlier phase of the intervention, with the 12-week assessing program impact at a later stage of the study.

	Behavior / Domain	Measure	Timepoints
1.	Socio-demographic questions	Measures adapted from GPRA and the National Survey on Drug Use and Health will include age, gender identity, race, ethnicity, sexual identity, and SES	Baseline only
2.	Treatment entry	Revised Supplemental Services Form	Baseline, 8-Week &12-Week Post Enrollment
3.	Relationship happiness	Relationship Happiness Scale	Baseline, 8-Week &12-Week Post Enrollment

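### Hypotheses b and c (relationship happiness; mood, physical illness and work functioning) are stated only as improvement from baseline in every arm, so their outcome cannot show what CRAFT adds over PEER

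*Protocol*

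**What the plan says.** Protocol section 1.2 lists one primary and four secondary hypotheses.

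- **b** (Relationship Happiness Scale, 2 and 3 months): "CSOs in all three groups will report that their relationship happiness has improved relative to baseline".
- **c** (POMS, SF12 and the SAS-SR work subscale, 2 and 3 months): "CSOs in all three groups will self-report that their own anxiety, depression, anger and physical illness has improved relative to baseline".
- **a** (treatment entry) ranks CRAFT-C above CRAFT-A and PEER, and CRAFT-A above PEER.
- **d** (CRAFT knowledge) predicts that the two CRAFT arms "will demonstrate higher fidelity of learning CRAFT principles as compared to the CSOs assigned to the standard condition (PEER").
- **e** expects similar high Usability scores in all groups, but ranks CRAFT-C highest on Usefulness.

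Section 1.3 lists relationship happiness and the participant's physical and mental health as secondary outcomes and attaches no contrast to them. Section 1.1 gives the general aim: to "assess the effectiveness of the adapted CRAFT protocols with WTV's business as usual model of Peer Support Forum (PEER"). Section 4.2 describes the two follow-up surveys by timing, "with the 12-week assessing program impact at a later stage of the study".

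**The concern.** The trial randomises to three arms, and its stated aim is to set CRAFT against PEER. For relationship happiness, mood, physical illness and work functioning, however, the only prediction is change within each arm. Such a change mixes any programme effect with whatever moves every participant over three months: regression to the mean in people who enrol when worried, the passage of time, or outside events. The protocol recognises one such influence, since section 4.2 adds questions on how COVID-19 affected the participant and the contact with the loved one.

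At stake is the interpretation of these secondary results. A report that b and c were confirmed could be read as evidence for CRAFT when it is not. A report that they were not confirmed could be read as evidence against CRAFT when it is not that either.

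**Working it through.** **1. Hypotheses side by side.**

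| Hypothesis | Outcome | Comparison stated |
|---|---|---|
| a | Treatment entry | Between arms |
| b | Relationship happiness | Within each arm, from baseline |
| c | Mood, physical illness, work functioning | Within each arm, from baseline |
| d | CRAFT knowledge | Between arms |
| e | Usefulness | Between arms |
| e | Usability | Similar and high in all arms |

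No other section of the protocol attaches a between-arm comparison to the scores in b and c.

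**2. What each result would mean.**

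- All three arms improve equally: b and c are true, and the CRAFT effect over PEER is zero.
- All three improve, CRAFT more: b and c are true, and the CRAFT effect is positive.
- Only the CRAFT arms improve: b and c are false as worded, and the CRAFT effect is positive.
- No arm improves: b and c are false, and the CRAFT effect is zero.

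True and false each go with both a zero and a positive effect, so the verdict on b and c does not identify the effect.

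**3. How easily a shared shift looks like improvement (illustration).** The protocol gives no SD, correlation, significance level or decision rule, so there is no figure to reproduce. Inputs: up to 84 participants (section 3.1: "For this pilot and feasibility study we plan to enroll up to 84 CSOs"), with equal groups intended (section 3.2: "to allow us to equal number of people in each group throughout the study recruitment period"), hence 84/3 = 28 per arm. Assumed: two-sided 5%, complete follow-up, baseline to follow-up correlation r of 0.5 or 0.7. The SD of change is √(2(1−r)), that is 1.000 or 0.775. For a shift of s SD common to all arms, the normal approximation to the chance of a significant improvement in one given arm at one timepoint is

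Φ( s√28 / √(2(1−r)) − 1.96 ).

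- s = 0.3: Φ(1.587 − 1.96) = 36% (r = 0.5); Φ(2.049 − 1.96) = 54% (r = 0.7).
- s = 0.5: 75% and 93%.

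The answer depends heavily on the rule. At s = 0.3, pooling all 84 participants gives 79% to 94%. Requiring p<0.05 in all three arms at both timepoints gives only 0.6% to 4% for b (simulation, same assumptions). The protocol fixes none of these rules, so no success rate for b or c can be quoted as a property of the plan.

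**4. What a randomised contrast would deliver.** The 95% half-width of a baseline-adjusted difference between two arms, in SD units, is t × √(2/n) × √(1−r²).

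- n = 28 (t = 2.006): 2.006 × 0.2673 = 0.536. Times 0.866 (r = 0.5) gives 0.46; times 0.714 (r = 0.7) gives 0.38.
- n = 21 (25% loss, assumed; t = 2.023): 0.54 and 0.45.

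The difference detectable with 80% power at n = 28 is 0.76 SD unadjusted, and 0.66 (r = 0.5) to 0.54 SD (r = 0.7) adjusted.

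Taking six scores (relationship happiness; POMS anxiety, depression and anger; SF12; SAS-SR work) gives 6 × 2 contrasts × 2 timepoints = 24 comparisons. With no true effects, 24 × 0.05 = 1.2 would be expected to have p<0.05. The count of six is an assumption: section 4.2 lists three SAS-SR sections, while hypothesis c names only the work subscale.

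**The case against.** The strongest reply is that nothing in b or c is false or contradictory. A hypothesis says what the investigators expect; it does not restrict what is estimated. Between-arm estimates for secondary scores are commonly set out in an SAP, which is not at hand. The aim in section 1.1 names none of these outcomes, and the remark on programme impact in section 4.2 mainly separates the 12-week survey from the 8-week one. All of this is fair and limits the point to a modest one. What remains is that the protocol does fix a criterion for these outcomes, that this criterion is within-arm, and that its neighbours in the same list compare arms.

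Four stronger readings are tempting, and the document does not support them.

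- *That predicting improvement under PEER is a mistake.* PEER is active support: section 4.1 says members draw on 12-Step strategies "or in CRAFT skills learned (usually from treatment programs or other We The Village members").
- *That none of the participant's own outcomes has a randomised comparison.* CRAFT knowledge (d) and Usefulness (e) are measured on the same people and do have one.
- *That a flat PEER arm would make b miss a real CRAFT effect.* If PEER does not improve, b is false, and failing to support it is correct. The fault is that b asks a different question, not that it loses power.
- *That a shared trend would usually confirm b and c.* That depends on a decision rule, and for c also a number of scales, that the protocol does not give.

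**Conclusion.** The point holds as a cheap improvement of modest importance. For relationship happiness, mood, physical illness and work functioning, the stated hypotheses cannot separate a CRAFT effect from change common to all arms, whichever way they turn out. This follows from the wording alone and needs no numerical assumption. The primary comparison and hypotheses d and e are untouched. The precision figures assume 28 per arm, complete follow-up and a correlation of 0.5 to 0.7; attrition would widen the intervals. At this size the randomised contrasts serve estimation, which suits a pilot, and cannot carry a confirmatory claim.

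**What to change.** Keep b and c and label them descriptive within-arm statements. Before outcomes are examined by arm, add to section 1.2 that for the Relationship Happiness Scale, POMS, SF12 and SAS-SR work scores the CRAFT-C versus PEER and CRAFT-A versus PEER differences at 8 and 12 weeks will be estimated, adjusted for the baseline score, and reported as exploratory with 95% confidence intervals. Name the scores, so that the number of comparisons is fixed and can be reported. If the SAP already contains these estimates, a reference to it in section 1.2 is enough.

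Cost: no new data, because all these scores are already scheduled at baseline, 8 and 12 weeks (section 4.2). The change would be a documented mid-study addition, since the consent addendum in section 6.2 shows that some participants are already in their programmes. It brings about 24 exploratory comparisons if six scores are used, and wide intervals. Some 8-week scores will be missing for participants who decline or do not answer the addendum, so the number contributing at each timepoint should be shown.
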